Detailed Protocol

Title: A pilot study to test the acceptability and feasibility of brief motivational interview intervention to help patients formulate their goals for medical care in the emergency department

Principal Investigator: [name], MPH

Funding: Emergency Medicine Foundation Career Development Award

Version Date: 5/12/2017

[figure not shown]
I. BACKGROUND AND SIGNIFICANCE

The majority (75%) of older adults with serious illnesses visit the ED during the last six months of life.¹ ED visits often mark an inflection point in these patients' illness trajectories, signaling a more rapid rate of decline.^{2,3} Many of these patients have not formulated and communicated their goals for end-of-life care,⁴ and the majority (56 to 99%) of older patients do not have advance directives available at the time of ED presentation.⁵ Most of these patients have priorities other than simply to live as long as possible,⁶ yet without alternative plans in place, they may receive aggressive care that does not align with their goals.⁷ Therefore, the ED provides a point in time and a location to identify and empower patients who would benefit from formulating and communicating their goals for future medical care.

Emergency medicine (EM) physicians recognize this opportunity and have expressed interest in engaging older adults with serious illnesses in a discussion of their end-of-life care;⁸ however, the time-pressured ED environment discourages physicians from conducting in-depth conversations with these patients.⁴ There is not yet a suitable brief intervention that is acceptable in the ED environment for physicians without extensive training in serious illness communication. Lack of a feasible method to intervene in the ED constrains our current clinical practice.

We propose to close this gap with a practical method to empower them to formulate their goals for end-of-life medical care. We are currently developing and refining the BMI intervention for serious illness communication (**Table1**). The BMI method allows physicians to engage patients in thinking about the importance of addressing a chronic care issue without conducting a time-consuming, sensitive conversation in the time-pressured ED environment. The BMI methods have been demonstrated robustly to improve outcomes for ED patients with alcohol and opioid abuse by helping patients understand the obstacles to and reasons for their medical care.⁹⁻¹² We are developing a BMI intervention to engage older adults in thinking about the importance of establishing care goals.

In this protocol, we will pilot test (Part I) the intervention to demonstrate its acceptability and feasibility in the ED, then collect patient-centered outcomes (Part II) on older adults with serious illness being discharged from the ED. This study will inform the study design of a future randomized clinical trial using this intervention.

| Table 1 Brief Motivational Interview ED Intervention to Facilitate Serious Illness Communication | |
|---------------------------------------------------------------------------------------------------------|---------------------------------------------------------------------------------------------------------------------------------------------------------------------------------------------------------------------------------------------------------------------------------------------------------------------------------------------------------------------------------------------------------------------------------------------------------------------------------------------------------------------------------------------------------------------------------------------------------------------------------------------------------------------------------------------------------------------------------------------------------------------------------------------------------------------------------------------------------------------------------------------------------------------------------------------------------------------------------------------------------------------|
| 1) Open | I'd like to talk about what is ahead with your illness after leaving the ED. Is that ok? |
| 2) Prognostic Awareness | What is your understanding of your _____ (serious illness)? |
| 3) Information & Feedback Elicit (Ask) Provide (Tell) Elicit (Ask) | 
Have you thought about preparing for your care in the future?
 
In the ED, we care for patients in the moment and also help them prepare for what's ahead after leaving the ED. Preparation helps patients and their caregivers adapt to an uncertain situation and relieve difficult decision making for caregivers.
 
How you think about these ideas of preparing about the future?
 |
| 4) Assess Importance Reinforce positives Ask about lower # | 
How important is it to prepare and think ahead about your future care?
  
You think it is __ (very / not very) important to think about this. That's great!
 
Why did you choose that number and not a lower one like a 1 or a 2?
 |
| 5) Worries & Strength Reflect & Summarize | 
What are your worries about planning for your future medical care?
 
What strengths in your life can you turn to for support in working through these questions about the future?
 
You are worried about ____, AND ____ gives you strength to plan for your future medical care.
 |
| 6) Action Plan Make a recommendation Thank patient | 
Based on what you said,
 
a. NOT ready (1-2) "This isn't the right time for you to think about your future care. I will recommend that your doctor asks you about this topic again at your next visit. Here is an information sheet that you may find helpful to read at home before your next visit with your doctor."
 
b. Somewhat ready (3-9) "I recommend that you explore what is important to you using Prepareforyourcare.org before your next visit with your doctor."
 
c. Completely ready (10) "I will work with your doctor about documenting your goals and preferences with your doctor on a medical record."
 
Let me write down steps that I would recommend for you and notify your doctor to let him/her know about your visit to the ED and our conversation today, to help him/her know where you are in your planning process. Is that okay?
 
Thank you for talking with me today.
 |

II. SPECIFIC AIM

Test the acceptability and feasibility of our brief motivational interview intervention to facilitate advance care planning (ACP) conversation on older adults with serious co-morbid illness being discharged from the emergency department (ED) and interview the participants to understand their perception and collect patient-reported outcomes data after leaving the ED.

Hypotheses

- a) $\geq 80\%$ of clinicians will find it acceptable to conduct this interview in the ED for appropriate patients;
- b) $\geq 80\%$ of patients will find the interview respectful to patient-oriented needs;
- c) $\geq 25\%$ of participants will have reported completing ACP conversation with their primary outpatient clinician at three month after leaving the ED.

Methodology

We will pilot test (Part I) the intervention to ED patients and interview 15 to 25 participants (depending on theme saturation) immediately following the intervention to explore how they perceived the intervention. After the intervention is administered, they will be asked to complete a Likert scale survey about acceptability. Additionally, we will collect pre-/post-intervention patient-centered outcome data (Part II) in-person at the time of intervention and via phone interview at three months after the ED visit for 100 patients.

III. SUBJECT SELECTION

Trained RAs will recruit the subjects using the inclusion and exclusion criteria (**Table 2**). We will use convenience sampling for this study. Each morning when a trained EM physician evaluates patients in the ED observation unit, the trained RAs will ask the physician to identify potential subjects based on inclusion and exclusion criteria.

| Inclusion | Exclusion |
|-------------------------------|--------------------------------------------------|
| ≥ 65 years of age | Acute physical or emotional distress |
| English-speaking | Determined by EM physician not to be appropriate |
| Capacity to consent | Clearly documented goals for medical care** |
| AND ≥ 1 Serious illness* | Already enrolled in this study |

*New York Heart Association stage 3 or 4 heart failure, oxygen-dependent chronic obstructive lung disease, chronic kidney disease on dialysis, and metastatic cancer. **MOLST, medical order for life sustaining treatment.

IV. SUBJECT ENROLLMENT

There are two subject types in this study – ED clinicians and ED patients. ED clinicians (attending physicians and physician assistants) will be recruited to train in and administer the proposed intervention on ED patients. After the intervention is administered, they will be asked to complete a Likert scale survey about acceptability. Clinicians will be asked to participate voluntarily. The PI will make an announcement at the faculty / physician assistant meetings and hand out the study information sheet. ED patients will be recruited to be interviewed after the intervention to learn their perception of the intervention. Upon identification of the

potential subject, the trained RAs will approach the potential subject to explain the study and ask about their willingness to participate. Once the eligible subject agrees to participate, the PI will consent the patient to enroll. After the trained RAs explain the study, the subjects will have time to think about the enrollment until the PI physically arrives in the ED. The PI will review all study elements again with the subjects to ensure understanding of the study. Upon enrollment, the trained physician responsible for the care of the patient will administer the intervention. When a trained physician is not on duty in the ED observation unit, the PI will administer the intervention.

There will be no other methods of recruiting for this study. Since this is a single-armed, pre-/post-intervention assessment study, there will be no treatment assignment or randomization.

V. STUDY PROCEDURES

There will be two distinct parts of the study: acceptability study (Part I) using qualitative interviews to explore the patient’s perception of the intervention and quantitative assessment of clinician’s acceptability rating, and feasibility study to measure patient-reported outcomes (Part II) after leaving the ED for future randomized clinical trial. The timing of proposed data collection is shown on Table 3.

| Table 3 Timing of Proposed Data Collection and Instruments | | | | |
|------------------------------------------------------------|------------|--------------------------------------------------------|-----------------------|--------------------------------------------------------|
| Study Part | Subjects | Pre-Intervention | Post-Intervention | Three Month Follow-up |
| Part 1 | Clinicians | | Acceptability Survey | |
| | Patients | | Qualitative Interview | |
| Part 2 | Patients | ACP Engagement Survey QUAL-E Survey IES-R Survey | | ACP Engagement Survey QUAL-E Survey IES-R Survey |

Part I: Acceptability Study

We will conduct in-depth, semi-structured interviews to understand patient’s perception of the intervention after its administration by a trained ED clinician. We anticipate to interview 15 to 25 patients, until thematic saturation of their perception is reached. Further, we will assess clinician acceptability by administering a Likert scale survey.

Measurements

Patient Perception Assessment: The PI and the trained RA will conduct the semi-structured interviews. The following domains will be explored: beliefs about formulating and communicating goals of care, experience of the ED intervention, and attitude towards further patient education about how to formulate goals of

care. Both the administration of BMI intervention by a clinician and subsequent qualitative interview of the participants will be video-recorded to ensure fidelity of the intervention administration and accurate capturing of their inputs.

Clinician Acceptability Assessment: Immediately after the clinician completes the encounter, we will ask to fill out an in-person survey to rate acceptability (Likert scale, 1 – not acceptable, 2 – somewhat unacceptable, 3 – neutral, 4 – somewhat acceptable, and 5 – acceptable).

Outcome Our primary outcome for the patient perception assessment of the study is to identify a recurring theme that illustrates the patient perception of the intervention. Our primary outcome for the physician assessment of the study is the proportion of administering clinicians who found the rating to be somewhat acceptable (4) or acceptable (5). Secondary outcomes are the time to administer the intervention and how often the 4 intervention components are appropriately completed.

Part II: Feasibility Study

We will collect pre-/post-intervention data to demonstrate the intervention's feasibility to improve patient-reported outcomes. We will measure patient-reported outcomes before (in-person) and three months after our intervention (over the phone). We will assess the proportion of participating older adults who self-reported having spoken to their primary outpatient physician and/or caregivers about their goals for end-of-life medical care following the intervention. We will use validated instruments to measure quality of life (QUAL-E),¹³ ACP engagement behavior (ACP Engagement Survey),¹⁴ patient empowerment (Patient Activation Measure – PAM™),¹⁵ and potential subjective distress caused by the intervention (a potentially traumatic event).¹⁶

Measurements

We will measure the proportion of patients who self-report having had the conversation with their outpatient physician. We will also use QUAL-E, a validated instrument to measure quality of life of patients with a range of diseases (cancer, congestive heart failure, chronic obstructive pulmonary disease, and end-stage renal disease).¹³ This instrument is particularly suited to measuring the quality of life of patients who may or may not have acknowledged the terminal nature of their disease, but who, nevertheless, are dealing with end-of-life issues. In addition, we will use the ACP Engagement Survey, a validated instrument developed based on Social and Behavior Change Theory, and it measures the full range of self-reported processes involved in ACP (e.g. changes in knowledge, contemplation, self-efficacy and readiness) as well as actions associated with ACP behavior.¹⁴ We will also use the PAM™, which is a validated instrument that measures the four stages of patient empowerment: (1) believing the patient role is important, (2) having the confidence and knowledge necessary to take action, (3) taking action to maintain and improve one's health, and (4) staying the course even under stress.¹⁵ To evaluate whether the ED intervention itself increases patient stress, we will also measure posttraumatic stress disorder symptoms using the Impact of Event Scale – Revised (IES-R).¹⁶ IES-R is a validated scale to assess subjective distress caused by traumatic events. The trained RAs will administer these instruments (see *Appendix*)

immediately before the intervention, and again by phone three months later. IES-R will only be used at three month.

Outcomes

The primary outcome is the proportion of patients self-reporting having spoken to their primary outpatient physician regarding their preferences for end-of-life medical care three months after the ED intervention. The secondary outcomes are quality of life, ACP behavior change, PAM™, posttraumatic stress disorder symptoms, proportion of subjects with documented ACP conversation on medical records three months after the intervention. We will also track the rate of patients being lost-to-follow-up to aid in appropriate design of a future randomized clinical trial.

VI. BIostatistical Analysis

Variables to be collected

We will collect demographic information of our subjects from the electronic health records, including age, gender, prior ACP documentation, co-morbid medical conditions, and ED diagnosis. Both the administration of BMI intervention by a clinician and subsequent qualitative interview of the participants will be video-recorded to ensure fidelity of the intervention administration and accurate capturing of their inputs. We will also administer the validated survey instruments (ACP Engagement Survey, QUAL-E, PAM™, IES-R) and self-reported completion of ACP conversation three months after leaving the ED.

Study Endpoint

Part I – Acceptability Study

The study will conclude when 15 to 25 participants are enrolled and thematic saturation of the qualitative analysis is reached.

Part II – Feasibility Study

The study will conclude when 100 participants are enrolled and three month post intervention data is collected over the phone.

Statistical Methods

Part I Analysis

We will employ a modified phenomenological approach to code for themes that illustrate patient's perception of the intervention. We selected phenomenology as our qualitative research strategy since it is particularly suited to explore how individuals experienced our intervention. The PI and the trained RA will immerse themselves in the text by reading and re-reading for content, quality, and patterns. During this time, the audit trail of notes will be kept by individual coders to be reviewed in a subsequent discussion group. After independent coding of 5 initial transcripts, the PI and the trained RA will determine the standard labeling for common patient perception themes; and these will be organized into a code book. We will iteratively re-organize the code book until the consensus is reached among the coders. If there are disagreements between the coders on a particular theme, we will employ a third coder to aid in judgment of the codes. The coders are

purposefully not blinded to the study questions because they need to decide what is pertinent to answer the study question at hand. The coders will use the code book to independently code the remaining transcripts. We will use Nvivo software to organize and manage our data. The study will conclude when new themes no longer emerge (thematic saturation is reached), based on agreement between the coders. If not, we will continue to recruit more subjects until thematic saturation is reached. The themes will be categorized and coders will decide with group consensus which quotes will be included as the representative quotes in the final manuscript. If there are disagreements, an additional researcher from the ED will be asked to review the quotes and themes.

Part II Analysis

We will calculate descriptive statistics of the patient-reported outcomes before and after the intervention. We will use one sample binomial exact test of proportions for categorical outcomes (e.g. proportion of patients reporting ACP conversations with their physicians), and Wilcoxon signed ranks test for ordinal outcomes (e.g. QUAL-E) at baseline and three months. We will use a p-value of 0.05 as the significance threshold.

Sample Size

Part I:

We propose to enroll 10 to 25 subjects in Part I ~~this pilot study~~. In prior qualitative studies, this is the general number that a study like this takes to reach thematic saturation. We may enroll more than 25 subjects if we find that thematic saturation has not reached. We will submit an amendment to change the enrollment number should that occur.

Part II:

We propose to enroll 100 subjects in Part II. A recent meta-analysis of advance directive documentation studies demonstrated improvement in ACP completion rate ranging from 2 to 44% with an intervention.¹⁷ We assume that the baseline rate of ACP completion rate is <10% to be conservative. Base on prior similar studies, we assume our intervention will result in 25% increase in the rate of conversation above 10%. A sample of 100 subjects will afford us 97% power (two-tailed alpha of 0.05) to detect a difference of the conversation completion rates of 10% before the intervention versus 30% after the intervention. Power is also expected to be strong for the ACP behavioral change scale outcomes (our secondary outcome, similar preliminary data demonstrated a pre-to-post improvement of 0.5 SD).¹⁸ With a conservative assumption, we will have 85–98% power with our sample size.

VII. RISKS AND DISCOMFORTS

There is no risks and discomforts associated with procedures, drugs, devices, or radiation in this study.

Psychosocial Risks (Uncommon)

The participants will be introduced or re-initiated on the topic of ACP. Some patients with serious illness do not wish to discuss ACP because they feel uncomfortable with the topic. This potential discomfort, however, is a part of the

routine practice of EM. Many ED clinicians discuss ACP with patients routinely, and the study does not add additional discomfort that is different from the routine clinical practice. Further, PI is trained in serious illness communication and will be available to manage patients' anxiety and other emotions as needed.

VIII. POTENTIAL BENEFITS

Potential Benefits to Participating Individuals

It is our hope that the proposed intervention will empower patients to engage in ACP discussions with their primary outpatient clinician $\geq 25\%$ of the time three months after the ED visit. Further, this intervention may also improve other patient-reported outcomes without causing significant harm.

Potential Benefits to Society

We hope that our intervention will allow EM clinicians to reach many older adults with serious illness presenting to the ED and guide them to formulate their goals for medical care. Such intervention will allow clinicians to align the future medical care towards end of life to match patients' values and preferences.

IX. MONITORING AND QUALITY ASSURANCE

The PI will be solely responsible for monitoring of safety, adverse events, protocol deviations, and outcomes. The data safety will be monitored by the PI on weekly basis, who is solely responsible for determining whether the research should be altered or stopped. The PI will be aware of every patient who is recruited and enrolled in the study. All data obtained in this study (video-recorded interviews of the participants and responses to the surveys by both clinicians and participants) will be stored in a secure Partners shared drive of the PI. As soon as the opportunity is available, the obtained data will be anonymized and removed of personal health information. All participants and clinicians will be de-identified and assigned research subject IDs (e.g. clinician 1). Only the study staff will have access to information that can link the subject IDs with the personal health information, which will be saved in the secure shared drive.

The PI will be aware of every subject enrolled in this study. Therefore, he is able to monitor for adverse events, such as unexpected emotional distress, and address them clinically using his clinical communication skills. Further, the PI will inform the IRB of any adverse events using standard procedures.

As stated earlier, the PI will be solely responsible for the adherence to the IRB-approved protocol. The PI will be checking the adherence on every enrollment (especially because he will physically be there).

X. REFERENCES

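### Hypothesis (b) predicts a proportion of at least 80% of patients, but the protocol defines only a thematic outcome for patients, so (b) cannot be evaluated as planned

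*Protocol*

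**What the plan says.** Section II (Specific Aim, Hypotheses) lists three predictions, each a proportion with a threshold. Hypothesis (b) is that at least 80% "of patients will find the interview respectful to patient-oriented needs".

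For Part I patients the protocol then specifies the following.

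- **Instrument.** Table 3 in Section V gives them one post-intervention entry, "Qualitative Interview". The acceptability survey is on the clinician row.
- **Content.** Section V, Part I, Measurements lists three interview domains. The one closest to (b) is "experience of the ED intervention". Respectfulness is not named.
- **Outcome.** The primary outcome for patient perception "is to identify a recurring theme that illustrates the patient perception of the intervention".
- **Analysis.** Section VI, Part I Analysis: "We will employ a modified phenomenological approach to code for themes". Recruitment continues until thematic saturation. No count of patients is described.

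Part I size is given as 15 to 25 in Sections II, V and VI (Study Endpoint), but as 10 to 25 in Section VI (Sample Size).

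**The concern.** A prediction that at least 80% of patients hold a view needs three things: a way to classify each patient, a rule for what counts as agreement, and a denominator. The protocol gives none of these for respectfulness. The outcome it does fix, a recurring theme, is a different kind of result. A theme can be prominent without its share of patients being known, and no theme can fall above or below 80%.

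The purpose of the pilot is to show acceptability and to inform a later randomized trial. If (b) is left as it is, the final report must either stay silent on one of three stated hypotheses or offer a proportion built after the fact from transcripts, with coding and counting rules chosen once the data are known.

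**Working it through.** The protocol states no sample size, power or significance level for (b), so it has no figure to reproduce. The check is a comparison of passages, followed by a calculation of what a proportion could show at the Part I sample size.

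**Step 1. Match each hypothesis to an outcome.**

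| Hypothesis (Section II) | Matching outcome | Classification rule |
|---|---|---|
| (a) at least 80% of clinicians find it acceptable | Proportion of administering clinicians (Section V, Part I, Outcome) | Rating of 4 or 5 on a defined 5-point scale |
| (b) at least 80% of patients find it respectful | None; the patient outcome is a theme | None |
| (c) at least 25% of participants report the conversation | "The primary outcome is the proportion of patients self-reporting having spoken to their primary outpatient physician" (Section V, Part II, Outcomes) | Self-report at three months; exact binomial test in Section VI |

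**Step 2. Look for a patient rating elsewhere.** Section V, Part II describes four instruments: the ACP Engagement Survey (engagement behaviour), QUAL-E (quality of life), PAM (empowerment) and the IES-R. None is described as rating how the interview was received. The nearest is the last: "IES-R is a validated scale to assess subjective distress caused by traumatic events". Distress and respect are different constructs.

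**Step 3. Settle who completes the Likert survey.** In Section II, Methodology, the Likert sentence follows one about interviewed participants, so its pronoun could be read as patients. The same sentence in Section IV follows a description of ED clinicians. Section V, Part I assigns the survey to clinicians, and Table 3 agrees. The Section II pronoun is therefore an ambiguity to correct. Even if patients did complete the survey, it would rate acceptability rather than respect, and no patient proportion is defined from it.

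**Step 4. What a proportion could show.** Suppose one scored item were asked of all n interviewed patients and x gave a favourable answer. The exact (Clopper-Pearson) 95% limits are

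- lower = 0.025 quantile of Beta(x, n − x + 1)
- upper = 0.975 quantile of Beta(x + 1, n − x)

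With x/n = 80%:

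| x/n | Exact 95% CI |
|---|---|
| 8/10 | 44.4 to 97.5% |
| 12/15 | 51.9 to 95.7% |
| 16/20 | 56.3 to 94.3% |
| 20/25 | 59.3 to 93.2% |

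The 8/10 row applies only if the 10-to-25 statement in Section VI governs.

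**Step 5. Could the threshold be tested?** If the true proportion were 80%, a unanimous result would have probability 0.8ⁿ: 0.107 at n = 10, 0.035 at n = 15, 0.012 at n = 20 and 0.004 at n = 25. At one-sided 0.025, even unanimity could not exclude 80% at 10 or 15 patients, and only unanimity could at 20 or 25. A proportion from Part I can therefore only be descriptive.

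**The case against.** The strongest reply is that the interview guide is not shown. Semi-structured interviews run from a guide, and a question about respect would fit the domain on experience of the intervention. This reply stands in part. A reader might infer that patients are never asked about respect, and the protocol does not support that inference. What it does support is narrower: no scored item, cut-off or count is specified, and the stated outcome remains a theme whatever the guide contains.

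A second reply is that Table 3 is poor evidence that something is absent. It omits PAM and the self-reported conversation, which is the Part II primary outcome, and it lists the IES-R before the intervention although the text says it is used only at three months. That is fair. The point does not depend on the table; the outcome and analysis text for Part I carries it.

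A third reply is that counting rules belong in a statistical analysis plan. Such a plan could define a count of coded themes. But the protocol has already fixed the patient outcome as a theme, and a response on a common scale from every patient has to be built into data collection.

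A reader might also infer that the answer to (b) would turn on a disputed denominator, either all interviewed patients or only those who mention respect. The wording of (b) refers to patients without restriction, so all interviewed patients is the natural denominator. It needs to be stated, but the protocol does not set two readings against each other.

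Finally, the stakes are modest: this is a single-arm pilot with a convenience sample, and no decision rule is attached to (b). That limits the weight of the point but does not remove the mismatch.

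**Conclusion.** The mismatch is real and follows from the protocol's own text. Of three stated hypotheses, only (b) has no outcome that can answer it. The conclusion rests on the Part I outcome and analysis sections and on the protocol's descriptions of the Part II instruments; it assumes nothing about the unseen interview guide.

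The consequence is limited to (b). Hypotheses (a) and (c) have matching proportion outcomes, and nothing here touches the Part II primary outcome or its power. The intervals in the working assume a single yes-or-no classification of every interviewed patient. They describe what the remedy could deliver and are not a measure of the defect. The correction should be made before enrolment, because a question that every patient must answer is hard to add later.

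**What to change.** Choose one of two changes.

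1. **Keep the threshold.** Add one scored respectfulness item to the Part I patient row of Table 3 and to the Part I outcomes in Section V. Ask it of every interviewed patient, within the interview already planned. State the cut-off in advance (for example 4 or 5 on a 5-point scale, as for clinicians) and name all interviewed patients as the denominator. Report the proportion descriptively with an exact 95% confidence interval. The research assistant should preferably give the item when the PI delivered the intervention, since Sections IV and V allow the PI to do both. Cost: one extra question, no added patient contact, and a wide interval to report.

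2. **Drop the threshold.** Restate (b) as a qualitative aim without the 80%. Cost: a change of wording. If respectfulness is also to be explored with every patient, the interview guide should say so.

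In either case, replace the ambiguous pronoun in the Likert sentence of Section II, Methodology with a reference to clinicians, and reconcile the two statements of Part I size (15 to 25 and 10 to 25), because under the first option that number sets the precision.

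### The one-sample test for the Part II primary outcome has no stated null value, and no reading of it fits both the target of at least 25% in hypothesis (c) and the stated 97% power

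*Protocol*

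**What the plan says.** Section II (Hypotheses) sets the target in hypothesis (c): at least 25% "of participants will have reported completing ACP conversation with their primary outpatient clinician at three month after leaving the ED". Section VIII repeats the same 25% as the hoped-for benefit to participants.

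Section V (Part II, Outcomes) makes that quantity primary, measured at three months: "The primary outcome is the proportion of patients self-reporting having spoken to their primary outpatient physician regarding their preferences for end-of-life medical care".

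Section VI (Part II Analysis) first plans descriptive statistics and then names the test: "We will use one sample binomial exact test of proportions for categorical outcomes", with the conversation proportion as its example. No null value is given. The sentence goes on to a Wilcoxon signed ranks test for ordinal outcomes and ends "at baseline and three months". The threshold follows: "We will use a p-value of 0.05 as the significance threshold".

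Section VI (Sample Size, Part II) says "We assume that the baseline rate of ACP completion rate is <10% to be conservative". It assumes an increase of 25% over that 10%. The rates used for power are not built on that increase; the stated aim is to "detect a difference of the conversation completion rates of 10% before the intervention versus 30% after the intervention". For these rates the section gives 97% power with 100 subjects at a two-sided alpha of 0.05.

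**The concern.** The hypothesis, the test and the power statement concern the same proportion but use different reference values. The hypothesis uses 25%, the power statement uses 10% against 30%, and the test uses none. No passage ties the 25% to a test, an interval or a success rule.

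The study is meant to inform the design of a randomised trial. If the test is run against 10%, observed rates from 17% to 24% would be statistically significant on the primary outcome while missing the study's own target. Because the protocol does not say which criterion counts, the choice could be made after the data are seen, and a significant p-value could be carried forward as support for hypothesis (c).

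**Working it through.** **Inputs from the protocol.** n = 100; two-sided alpha 0.05; assumed baseline 10%; rate after the intervention 30% (all Section VI, Sample Size); target 25% (Section II). X is the number reporting the conversation, binomial(n, p). Unless stated otherwise, all 100 patients are taken as evaluable.

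**1. The stated 97% power.**
- One-sample exact test, null 10%: power = P(X ≥ 17 | p = 0.30) = 0.999. This is not 97%.
- Two independent samples of 100, 10% against 30%, pooled normal approximation: 94.8% two-sided, 97.5% one-sided.
- Paired (McNemar) test on 100 pairs: power = Φ[(0.20·√100 − 1.96·√d) / √(d − 0.20²)], where d is the discordant proportion. The protocol does not give d, so a range is shown:
  - d = 0.20 (nobody switches from yes to no): 99.8%
  - d = 0.30 (5% switch from yes to no): (2 − 1.96·0.548)/√0.26 = 1.82, giving 96.5%
  - d = 0.34 (before and after independent): 94.1%

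The 97% is therefore closer to a two-sample or before/after calculation than to the one-sample test that is named.

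**2. Reading A: null = 10%.**
- P(X ≥ 17 | 0.10) = 0.0206. Two-sided p = 0.041 (doubled tail) or 0.028 (minimum likelihood).
- P(X ≥ 16 | 0.10) = 0.0399. Two-sided p = 0.080 or 0.064, not significant.
- The cut-off is 17/100, exact 95% CI 10.2% to 25.8%. The estimate is 8 points below target.
- Illustration at an assumed true rate of 20% (not a protocol figure): P(X ≥ 17) = 0.808 and P(X ≥ 25) = 0.131, so P(17 ≤ X ≤ 24) = 0.676. Of the significant results, 0.676/0.808 = 84% would miss 25%.
- With fewer evaluable patients (assumed range, doubled tail) the cut-off is 16/90 (17.8%), 15/80 (18.8%), 13/70 (18.6%) or 12/60 (20.0%). All are below 25%.

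**3. Reading B: null = 25%.**
- P(X ≥ 35 | 0.25) = 0.0164, doubled 0.033. The exact 95% CI for 35/100 is 25.7% to 45.2%, so 35/100 is the smallest count whose lower limit exceeds 25%.
- Power at a true 30% = P(X ≥ 35 | 0.30) = 0.163. At a true 35% it is 0.538.
- The minimum-likelihood version rejects already at 34/100 (p = 0.0487), although the exact interval (24.8% to 44.2%) still contains 25%. Power at 30% is then P(X ≥ 34 | 0.30) = 0.221. Neither version is near 97%.

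**4. Reading C: a before/after comparison.** This tests whether the rate changed. A true rise from 10% to 20% would be a real change and would still miss 25%.

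**5. Reading D: 25% as a descriptive benchmark on the estimate.** P(X ≥ 25) is 0.131 at a true 20%, 0.538 at 25%, 0.886 at 30% and 0.988 at 35%. An observed 25/100 has exact 95% CI 16.9% to 34.7%.

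**6. The sample-size figures among themselves.** A 25% increase over 10% is 10 + 25 = 35% in percentage points, or 10 × 1.25 = 12.5% in relative terms. Neither is the 30% used for power, and neither is the 25% of hypothesis (c).

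**The case against.** A reader might infer that the protocol fixes the test against 10% and so never tests hypothesis (c). The protocol does not support that as fact. Part II Analysis states no null, and the 10% appears only in the sample-size text. The study is described as a pre-/post-intervention assessment, the power statement is worded as before against after, and 97% fits such a comparison better than the one-sample test. A null of 25% is not excluded either. The null value and the success rule could also be left to a statistical analysis plan, which is not at hand.

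The 25% may also be only a descriptive benchmark. It stands beside two 80% targets that have no inferential test, Section VIII expresses it as a hope, and descriptive statistics are planned, so an observed 17% would visibly miss it. No passage says that p < 0.05 establishes hypothesis (c) or triggers the next trial.

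Most of this stands, and it limits how strongly the point can be put. It does not remove the point. The protocol itself fixes a hypothesis, a test, a threshold and a power figure for one proportion, and an analysis plan would have to choose among statements that do not agree. The benchmark reading is reasonable, but the protocol does not state it.

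**Conclusion.** The point holds in a conditional form. No single reading fits the target of at least 25%, the one-sample test and the 97% power together. With a null of 10%, significance starts at 17/100 and does not support hypothesis (c). With a null of 25%, power at the protocol's own 30% is about 16% (22% under the minimum-likelihood version). A before/after test leaves 25% unaddressed.

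The 17% cut-off rests on two assumptions: a null of 10%, which is inferred, and 100 evaluable patients. With 60 to 90 evaluable it is about 18% to 20%. The 81% and 68% figures rest on an assumed true rate of 20%. The stronger statement, that the plan definitely tests against 10% and leaves hypothesis (c) untested, goes beyond the text.

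Severity: should be fixed. Confidence: moderate.

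**What to change.** In Section VI, Part II Analysis:
- State the null value of the one-sample exact test.
- Report the three-month proportion with its exact 95% CI.
- State that hypothesis (c) is a pilot benchmark, judged on the estimate against 25% with the interval shown.
- State that rejecting 10%, if that is the null, is supportive only and does not establish hypothesis (c).

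In Section VI, Sample Size, reconcile the 25% target, the 30% used for power and the assumed 25% increase over 10%. State which test the power figure belongs to and recompute it for that test.

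The cost is about one paragraph of analysis text and a corrected sample-size paragraph, with no added patients, visits or data. The downside is a less favourable success statement: at a true 30%, the chance of observing at least 25% is 89%, against 99.9% for rejecting 10%.
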